8.3.2 Safety analysis set

All randomized patients receiving at least 1 dose of study treatment will be considered in the safety population and included in the safety analysis.

8.4 Outcome measures for analyses

8.4.1 Primary efficacy endpoint

The primary efficacy endpoint is the change in HbA1c from baseline to Week 28.

8.4.2 Secondary efficacy endpoints

- Change in total body weight from baseline to Week 28
- Change in FPG from baseline to Week 28
- Change from baseline in 2-hour PPG after standardized MTT at Week 28
- Proportion of patients achieving HbA1c <7.0% at Week 28
- Proportion of patients achieving weight loss ≥ 5 .0% at Week 28
- Change from baseline in FPG to Week 2 (dapagliflozin+exenatide vs exenatide)
- Change from baseline in seated systolic BP from baseline to Week 28

8.4.3 Exploratory endpoints

- Proportion of patients rescued or discontinued for lack of glycemic control at Week 28

- Proportion of patients achieving HbA_{1c} $\leq 6.5\%$ at Week 28.
- Change in self monitored 6-point blood glucose from baseline to Week 28
- Proportion of patients with HbA_{1c} reduction $\geq 1.0\%$ at Week 28
- Proportion of patients with HbA_{1c} reduction $\geq 1.0\%$ and weight reduction $\geq 3.0\%$ at Week 28
- Change in waist circumference compared to baseline at Week 28
- Change in HOMA B (beta cell function) and HOMA S (insulin sensitivity) scores at Week 28
- Proportion of patients with a reduction in both HbA_{1c} and weight at Week 28
- Change in diastolic BP from baseline to Week 28
- Change in total cholesterol, LDL cholesterol, HDL cholesterol, non-HDL cholesterol, and fasting triglycerides from baseline to Week 28
- DTSQ-s and SHIELD WQ-9 questionnaire at Week 28
- Change in total body weight in patients without an AE of nausea from baseline to Week 28
- Exenatide and dapagliflozin PK profiles

8.4.4 Extension Period 1 exploratory endpoints

- Change in HbA_{1c} from baseline to Week 52.
- Change in total body weight from baseline to Week 52.
- Change in FPG from baseline to Week 52.
- Change in 2-hour PPG after a standardized meal tolerance test at Week 52.
- Proportion of patients achieving HbA_{1c} $< 7.0\%$ at Week 52.
- Proportion of patients achieving weight loss $\geq 5.0\%$ at Week 52.
- Change in seated systolic BP from baseline to Week 52.

- Proportion of patients rescued or discontinued for lack of glycemic control at Week 52.
- Proportion of patients achieving HbA1c $\leq 6.5\%$ at Week 52.
- Change in self-monitored 6-point blood glucose from baseline to Week 52.
- Proportion of patients with HbA1c reduction $\geq 1.0\%$ at Week 52.
- Proportion of patients with HbA1c reduction $\geq 1.0\%$ and weight reduction of $\geq 3.0\%$ at Week 52.
- Change in waist circumference compared to baseline at Week 52.
- Change in HOMA B (beta cell function) and HOMA S (insulin sensitivity) scores at Week 52.
- Proportion of patients with a reduction in both HbA1c and weight at Week 52.
- Change in diastolic BP from baseline to Week 52.
- Change in total cholesterol, LDL cholesterol, HDL cholesterol, non-HDL cholesterol, and fasting triglycerides from baseline to Week 52.
- DTSQ-s and SHIELD-WQ-9 questionnaires at Week 52.
- Change in total body weight in patients without an AE of nausea from baseline to Week 52.

8.4.5 Extension Period 2 exploratory endpoints

- Change in HbA1c from baseline to Week 104.
- Change in total body weight from baseline to Week 104.
- Change in FPG from baseline to Week 104.
- Change in 2-hour PPG after a standardized meal tolerance test at Week 104.
- Proportion of patients achieving HbA1c $< 7.0\%$ at Week 104.
- Proportion of patients achieving weight loss $\geq 5.0\%$ at Week 104.
- Change in seated systolic BP from baseline to Week 104.

- Proportion of patients rescued or discontinued for lack of glycemic control at Week 104.
- Proportion of patients achieving HbA_{1c} \leq 6.5% at Week 104.
- Change in self-monitored 6-point blood glucose from baseline to Week 104.
- Proportion of patients with HbA_{1c} reduction \geq 1.0% at Week 104.
- Proportion of patients with HbA_{1c} reduction \geq 1.0% and weight reduction of \geq 3.0% at Week 104.
- Change in waist circumference compared to baseline at Week 104.
- Change in HOMA B (beta cell function) and HOMA S (insulin sensitivity) scores at Week 104.
- Proportion of patients with a reduction in both HbA_{1c} and weight at Week 104.
- Change in diastolic BP from baseline to Week 104.
- Change in total cholesterol, LDL cholesterol, HDL cholesterol, non-HDL cholesterol, and fasting triglycerides from baseline to Week 104.
- DTSQ-s and SHIELD-WQ-9 questionnaires at Week 104.
- Change in total body weight in patients without an AE of nausea from baseline to Week 104.

8.5 Methods for statistical analyses

8.5.1 Analysis of the primary variable

The primary analysis will assess the benefit (superiority) of the combination of EQW + dapagliflozin over the individual components (ie, over EQW and over dapagliflozin) for the change in HbA_{1c} from baseline to Week 28 of the short-term double-blind treatment period for the ITT population.

The mixed model for the repeated measures (MMRM) will include change from baseline to Week 28 in HbA_{1c} as the dependent variable, treatment, region, baseline HbA_{1c} stratum ($<9.0\%$ or $\geq 9.0\%$), week, and treatment by week interaction as fixed factors. Baseline measurement of HbA_{1c} will be included as a continuous covariate. All observed HbA_{1c} values from post-baseline (including early dropouts, but excluding those data points after glycemic rescue therapy or post-treatment follow-up) will be included in the MMRM analysis. Since MMRM will be used for the primary analysis of primary endpoint, there will be no need

to impute missing data. Consequently, no Last Observation Carried Forward or other imputation technique will be required or used for the primary analysis. An unstructured covariance matrix will be used for the MMRM analysis, unless the model does not converge, in which case the covariance structure will be decided based on model convergence status and the Akaike information criterion. The least-squares (LS) means, standard errors, and 2-sided 95% confidence intervals, as well as the mean difference between treatment groups (EQW + dapagliflozin compared to EQW and compared to dapagliflozin) will be presented.

The treatment comparison of the primary efficacy endpoint (HbA1c change from baseline) will be considered significant if and only if the comparisons of the combination treatment group (EQW + dapagliflozin) against both of the 2 active-control groups (dapagliflozin 10 mg QD and EQW 2 mg) are significant. Due to this specific criterion for showing superiority of the combination treatment group over the individual treatment groups in primary endpoint, no multiplicity adjustment for the primary analysis will be required to control the overall type-I error, which is considered to be 0.05; consequently, both of the individual treatment comparisons will be performed at 5% level of significance (ie, $\alpha = 0.05$ 2-sided).

The same MMRM analysis will be applied to the PP population as a supportive analysis for the primary efficacy endpoint.

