- Standard deviation of 1.1% and 90% power (based on a 2-sample t-test at a 0.05 significance level)

Assuming a 5% drop-out rate prior to Week 4 (Visit 6), the first visit where HbA1c is tested, 220 patients per treatment arm (a total of approximately 660 patients) would have post-baseline measurements of HbA1c and thus be included in the ITT analysis of the primary objective. Assuming 40% screen failure, a total of 1100 patients will be screened.

Statistical analysis methods

The primary analysis will assess the benefit (superiority) of the combination of EQW + dapagliflozin over the individual components (ie, over EQW and over dapagliflozin) for the change in HbA1c from baseline to Week 28 of the short-term double-blind treatment period for the ITT population.

The mixed model for the repeated measures (MMRM) will include change from baseline to Week 28 in HbA1c as the dependent variable, treatment, region, baseline HbA1c stratum ($<9.0\%$ or $\geq 9.0\%$), week, and treatment by week interaction as fixed factors. Baseline measurement of HbA1c will be included as a continuous covariate. All observed HbA1c values from post-baseline (including early dropouts, but excluding those data points after glycemic rescue therapy or post-treatment follow-up) will be included in the MMRM analysis. Since MMRM will be used for the primary analysis of primary endpoint, there will be no need to impute missing data. Consequently, no Last Observation Carried Forward or other imputation technique will be required or used for the primary analysis. An unstructured covariance matrix will be used for the MMRM analysis, unless the model does not converge, in which case the covariance structure will be decided based on model convergence status and the Akaike information criterion. The least-squares (LS) means, standard errors, and 2-sided 95% confidence intervals, as well as the mean difference between treatment groups (EQW + dapagliflozin compared to EQW and compared to dapagliflozin) will be presented.

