3.1 Inclusion criteria

For inclusion in the study patients should fulfill the following criteria:

1. Provision of informed consent prior to any study specific procedures.
2. Is able to read, understand, and sign the Informed Consent Forms (ICFs) and, if applicable, an Authorization to Use and Disclose Protected Health Information form (consistent with Health Insurance Portability and Accountability Act of 1996 [HIPAA] legislation), communicate with the investigator, and understand and comply with protocol requirements.
3. Is at least 18 years old at Screening; the upper age limit should be based on local metformin label restrictions.
4. Has a diagnosis of T2DM.
5. Has HbA1c of 8.0% to 12.0%, inclusive, at Visit 1 and Visit 2.
6. Treated with a stable dose of metformin 500 mg/day for at least 2 months prior to Screening.
7. Is male, or is female and meets all the following criteria:
 - Not breastfeeding.
 - Negative pregnancy test result (human chorionic gonadotropin, beta subunit [β hCG]) at Visit 1 (Screening) (not applicable to hysterectomized females).
 - If of childbearing potential (including perimenopausal women who have had a menstrual period within 1 year), must practice and be willing to continue to

practice appropriate birth control (defined as a method which results in a low failure rate, ie, less than 1% per year, when used consistently and correctly, such as implants, injectables, hormonal contraceptives [pills, vaginal rings, or patches], some intrauterine contraceptive devices [levonorgestrel-releasing or copper-T], tubal ligation or occlusion, or a vasectomized partner) during the entire duration of the study. As applicable, all methods must be in effect prior to receiving the first dose of study medication.

- Must practice appropriate birth control as stated above for 10 weeks after the last dose of study medication.

8. Patients who are receiving the following medications must be on a stable treatment regimen for a minimum of 2 months prior to Visit 1 (Screening):

- Antihypertensive agents
- Thyroid replacement therapy
- Antidepressant agents.

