4.2 Treatment period

After the randomization visit (Visit 3), patients will complete study visits at 1- to 4-week intervals until the end of the randomized treatment period (Visit 12, Week 28). Starting at Week 8, patients with inadequate glycemic control based on progressively stricter glycemic criteria as outlined in [Table 3](#) will remain in the study and will receive open-label rescue therapy with basal insulin.

Table 3 **Criteria for initiation of rescue therapy during the randomized treatment period**

Period	Central laboratory FPG
From Visit 7/Week 8, inclusive, up to and including the day before Visit 8/Week 12	FPG >270 mg/dL (15 mmol/L)
From Visit 8/Week 12, inclusive, up to and including the day before Visit 10/Week 20	FPG >240 mg/dL (13.2 mmol/L)
From Visit 10/Week 20, inclusive, up to and including Visit 12/Week 28 and all unscheduled visits through the day prior to Visit 13/Week 36	FPG >200 mg/dL (11.1 mmol/L)

Note: Repeat FPG testing required for confirmation before rescue initiated.

Abbreviation: FPG fasting plasma glucose

Patients with a central laboratory FPG value meeting the lack of glycemic control criterion at a pre-specified visit will be scheduled for a follow-up visit (within 3 to 5 days) to obtain a second central laboratory FPG value and review the patient's glucose meter readings. If the repeat central laboratory FPG value still meets the criterion, the patient may receive rescue therapy. Patients should continue receiving study medication while receiving rescue therapy. Patients who meet rescue criteria in the double-blind treatment period must first complete the Rescue visit procedures before receiving open-label rescue therapy, to ensure that important trial endpoint measurements are collected.

Patients who receive rescue therapy should be instructed to perform the 6-point SMBG profile before returning to the clinic for the Rescue Visit; see Section 5.1.5 for additional details.

Rescued patients with central laboratory HbA1c values >8.0% despite a maximum tolerated dose of rescue therapy for 12 weeks will be discontinued from the study and referred for additional antihyperglycemic therapy.

4.2.1 Treatment Period Visits (Visits 4 to 11, Weeks 1, 2, 4, 8, 12, 16, 20, and 24)

Prior to these visits, patients are to have fasted overnight (at least 8 hours). Patients should delay administering their morning dose of metformin and study medication on the morning of the study-site visit.

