The following will be performed during these visits:

- IVRS will be contacted to register the visit.
- AEs, potential CV event triggers (Section 6.8.1), and concomitant medications will be reviewed.
- A brief physical exam will be conducted (refer to Section 5.2.2).

- Vital signs (sitting systolic and diastolic BP and HR) will be assessed.
- Body weight will be measured.
- Blood samples will be collected **prior to administration of study medication** for the following assessments:
 - Chemistry and hematology
 - HbA1c (Visits 6, 7, 8, 9, 10, and 11 only)
 - Fasting plasma glucose will be collected at all treatment visits (need for rescue will be evaluated at Visits 7 to 11 only)
 - Serum creatinine (calculated creatinine clearance; Cockcroft-Gault formula)
 - Serum antibodies to exenatide (Visits 6, 7, 8, and 10 only)
 - Plasma exenatide and dapagliflozin (Visits 6, 7, 8, and 10 only).
- Urine will be collected for the following assessments:
 - Urinalysis
 - Urine glucose/creatinine ratio
 - Pregnancy test for all female patients, unless patient has had a hysterectomy.
- Patient diary will be reviewed.
- Visit 11 only: Patients will be instructed to perform 6-point SMBG on any 3 days in the week prior to Visit 12.
- Hypoglycemia episodes will be assessed.
- Diet and exercise counseling will be provided.
- Glucose meter and supplies will be provided.
- Study medication compliance will be reviewed.
- Study medication will be dispensed every 4 weeks during the treatment period: Visits 6 to 11. Study site personnel will monitor administration of injectable study medication (if the patient is due for an injection at the time of the visit).

- Instructions, reminders, and supplies (as appropriate) will be given to the patient (or designated caregiver) for proper transportation and storage of the study medication (to ensure temperature control, etc.).
- Rescue medication will be dispensed at Visits 7 to 11 if criteria for rescue medication are met (refer to [Table 3](#)).
- Used/unused study medication will be collected every 4 weeks (Visits 6 to 11).

4.2.2 End of Treatment Period Visit (Visit 12, Week 28) or Early Termination or Rescue during Treatment Period

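### The primary MMRM imposes one baseline-HbA1c slope on every visit from Week 4 to Week 28, which costs precision at Week 28 if that slope steepens over time

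*Protocol*

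**What the plan says.** Section 8.5.1 gives the fixed factors as treatment, region and baseline HbA1c stratum, followed by "week, and treatment by week interaction as fixed factors". It then adds: "Baseline measurement of HbA_{1c} will be included as a continuous covariate". The synopsis repeats this: "Baseline measurement of HbA1c will be included as a continuous covariate". Neither place names a baseline-by-week or stratum-by-week term, and neither leaves these terms to the SAP.

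Four other statements bear on the point:

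- Covariance (8.5.1): "An unstructured covariance matrix will be used for the MMRM analysis, unless the model does not converge".
- Data left out (8.5.1): the model uses all observed post-baseline values, "excluding those data points after glycemic rescue therapy or post-treatment follow-up".
- HbA1c schedule (4.2.1): "HbA1c (Visits 6, 7, 8, 9, 10, and 11 only", that is Weeks 4, 8, 12, 16, 20 and 24. Week 28 (Visit 12) makes seven post-baseline visits.
- Rescue (4.2): "Starting at Week 8, patients with inadequate glycemic control based on progressively stricter glycemic criteria" receive rescue. Table 3 states those criteria as central-laboratory FPG.

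The entry criterion in 3.1 is "Has HbA1c of 8.0% to 12.0%, inclusive, at Visit 1 and Visit 2", so baseline HbA1c has a wide spread.

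**The concern.** HbA1c responds slowly. At Week 4 the change is incomplete, so baseline may predict it only weakly. By Week 28 patients who started at 11 or 12% have had time to fall much further than those who started at 8%. A model with a single slope cannot represent both. Under an unstructured covariance the fitted slope is a generalised least-squares average that gives most weight to visits with small variance, and those tend to be the early ones. The primary contrast is at Week 28, so the adjustment it receives may be set largely by visits that carry no primary inference.

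Mainly, precision is at stake. A second effect is possible: if patients with a high baseline leave the analysis through rescue more often in one arm than another, an ill-fitting slope no longer corrects for the resulting imbalance.

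**Working it through.** **Planning figure.** Inputs from section 8.2: difference 0.35, SD 1.1, power 90%, two-sample t-test at 0.05 (two-sided per 8.5.1).

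- Normal approximation: n = 2 × (1.960 + 1.282)² × 1.1² / 0.35² = 207.6, so 208 per group.
- Exact t-test: 208 gives power 0.899 and 209 gives 0.901. The stated 209 is reproduced.
- 209 / 0.95 = 220 per arm, 660 in total, and 660 / 0.6 = 1100 screened.

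This calculation takes no credit for baseline adjustment.

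**Mechanism.** Let β be the vector of true baseline slopes over the seven visits, Σ the residual covariance and s the baseline SD. In large samples the common slope is

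b = (1′S⁻¹β) / (1′S⁻¹1), with S = Σ + s²(β − b1)(β − b1)′, iterated until stable.

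The Week 28 variance relative to a model with visit-specific slopes is

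1 + s²(β₂₈ − b)² / σ₂₈².

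The protocol gives no slopes, so these inputs are assumed: s = 1.0, σ₂₈ = 1.0, correlation 0.9 between adjacent visits, and slopes and residual SDs linear across the visits.

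| Slope, Week 4 to 28 | Residual SD, Week 4 to 28 | Common slope b | Week 28 variance ratio |
|---|---|---|---|
| −0.2 to −0.5 | 0.4 to 1.0 | −0.167 | 1 + 0.333² = 1.11 |
| −0.2 to −0.5 | 0.6 to 1.0 | −0.216 | 1 + 0.284² = 1.08 |
| −0.2 to −0.5 | 1.0 throughout | −0.350 | 1 + 0.150² = 1.02 |
| −0.15 to −0.7 | 0.4 to 1.0 | −0.089 | 1 + 0.611² = 1.37 |
| −0.3 throughout | 0.4 to 1.0 | −0.300 | 1.00 |

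The loss needs a slope that changes, and it is much larger when early visits are less variable.

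**Simulation of precision.** Three arms of 209, seven visits, unstructured covariance, 500 trials per scenario, true effect −0.35. Assumptions not in the protocol: baseline mean about 9.3 and SD about 1.1, adjacent-visit correlation 0.92, 2% drop-out per visit, and region omitted. Without rescue:

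| Slope, Week 4 to 28 | Fitted common slope | SE as written | SE with baseline- and stratum-by-week | Variance ratio | Power, one comparison |
|---|---|---|---|---|---|
| −0.2 to −0.5 | −0.10 | 0.1066 | 0.0999 | 1.14 | 0.89 vs 0.94 |
| −0.15 to −0.7 | +0.03 | 0.1118 | 0.0886 | 1.59 | 0.89 vs 0.99 |
| −0.3 throughout | −0.30 | 0.1069 | 0.1069 | 1.00 | 0.91 vs 0.90 |

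The ratios are (0.1066/0.0999)² = 1.14 and (0.1118/0.0886)² = 1.59. With constant slopes the extra terms cost essentially nothing.

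Success requires both comparisons. With a 0.35 effect for each, correlation 0.5 from the shared arm and a normal approximation, the first scenario gives joint power of about 0.84 as written and 0.89 with the added terms.

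**Simulation of bias.** Rescue was made to depend on baseline and to differ by arm.

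| Slope, Week 4 to 28 | Week 28 missing, combination vs comparators | As written | With added terms | Paired shift (Monte Carlo SE) |
|---|---|---|---|---|
| −0.2 to −0.5 | 18% vs 32% | −0.368 | −0.349 | −0.019 (0.002) |
| −0.15 to −0.7 | 18% vs 32% | −0.378 | −0.352 | −0.026 (0.003) |
| −0.2 to −0.5 | 13% vs 17% | −0.353 | −0.351 | −0.002 (0.002) |
| −0.15 to −0.7 | 13% vs about 17% | −0.357 | −0.354 | −0.003 (0.003) |
| −0.3 throughout | 18% vs about 32% | −0.350 | −0.350 | 0.000 |

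The shift is distinguishable from zero only under heavy differential rescue, where it favours the combination.

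**The case against.** A main-effect baseline covariate contradicts nothing in the protocol, and every consequence above rests on slopes, variances and rescue rates that the protocol does not give. With a constant slope there is no loss at all. This stands: the size is conditional.

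A reader might infer that the written model leaves the trial underpowered. The protocol does not support that. Section 8.2 sizes the trial on an unadjusted t-test, and simulated power under the written model stayed at about 0.86-0.93 per comparison across the steepening-slope scenarios. What is lost is efficiency beyond the plan.

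A reader might also infer that the primary estimate will be materially biased. That is not supported either. Baseline dependence of rescue alone, equal across arms, should not bias the difference. Rescue follows FPG, with repeat confirmation and only from Week 8 (section 4.2, Table 3), and patients with FPG of 280 mg/dL or more are excluded at entry (3.2). The link to baseline HbA1c is therefore indirect and unquantified.

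Finally, section 8.5.8 plans sensitivity analyses and names ANCOVA as an example. A Week 28 ANCOVA adjusted for baseline would fit a Week 28 slope and could reveal disagreement. That is a useful check, but it leaves the primary model as it is.

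**Conclusion.** The point holds as a worthwhile, nearly free improvement to a model that the protocol itself fixes. It is not an error that threatens the trial.

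- **Precision.** Week 28 variance rises by roughly 1-20% in moderate scenarios and up to about 50-60% in extreme ones. This assumes a baseline slope that steepens between Week 4 and Week 28. If early visits are no less variable than late ones, the loss for moderate slopes is only a few per cent. If the slope is constant, it is zero.
- **Bias.** It was at most about 0.03 HbA1c points against a planned effect of 0.35, and 0.003 or less with lighter rescue. It arises only if slopes change over time and rescue or drop-out both depends on baseline and differs by arm.
- **Power.** The planned 90% per comparison is broadly kept.

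Confidence is high on what the model contains and on the mechanism. It is lower on the size, because no slopes are documented. The finding is confined to the primary model. Section 8.5.2 names MMRM or ANCOVA for the continuous secondary endpoints but lists no terms, so nothing is misstated there.

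**What to change.** In section 8.5.1 and the matching synopsis paragraph, add baseline HbA1c-by-week and baseline HbA1c stratum-by-week to the fixed effects of the primary MMRM. Keep the other terms, the covariance rule and the data rules unchanged.

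With seven visits each interaction uses 6 degrees of freedom, so the cost is up to 12 with about 660 patients randomized. No procedure, visit or sample size changes. The change should be made before the unblinding at the Week 28 database lock, since altering the primary model afterwards would look data-driven.
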